3.5 CRITERIA FOR REMOVAL FROM PROTOCOL THERAPY AND OFF STUDY CRITERIA

Prior to removal from study, effort must be made to have all subjects complete a safety visit approximately 30 days following the last dose of study therapy.

3.5.1 Criteria for removal from protocol therapy

- Progressive disease
- Participant requests to be withdrawn from active therapy
- Unacceptable Toxicity as defined in Section [3.1](#)
- Investigator discretion
- Positive pregnancy test
- Procedure failure (incapacity to do apheresis or obtain intraperitoneal access)
- Lost to follow-up
- Intercurrent illness

3.5.2 Off-Study Criteria

- Completed study follow-up period
- Participant requests to be withdrawn from study
- Death
- Starting alternative therapy
- Refused follow-up
- Procedure failure
- Screen failure
- Lost to follow-up

3.5.2.1 Lost to Follow-up

A participant will be considered lost to follow-up if he or she fails to return for two scheduled visits and is unable to be contacted by the study site staff.

The following actions must be taken if a participant fails to return to the clinic for a required study visit:

- The site will attempt to contact the participant within 72 business hours in order to reschedule the missed visit and will counsel the participant on the importance of maintaining the assigned visit schedule and ascertain if the participant wishes to and/or is eligible to continue in the study.
- Before a participant is deemed lost to follow-up, the investigator or designee will make every effort to regain contact with the participant (where possible, 3 telephone calls and, if necessary, a certified letter to the participant's last known mailing address or local equivalent methods). These contact attempts should be documented in the participant's medical record or study file.
- Should the participant continue to be unreachable, he or she will be considered to have withdrawn from the study with a primary reason of lost to follow-up.

4 CONCOMITANT MEDICATIONS/MEASURES

4.1 PROHIBITED MEDICATIONS

- No concomitant use of alternative, complementary therapies or over-the-counter agents will be allowed without approval of the PI. All medications must be recorded in the case report form and be reviewed by the treating physician at each visit.
- Oral anticoagulants such as warfarin are not contraindicated provided that there is increased vigilance with respect to monitoring INR. If medically appropriate, low molecular weight heparin may be considered preferable to warfarin, due to shorter half-life and more predictable anticoagulant effect.
- Caution should be exercised in the concomitant use of any medication that may markedly affect renal or hepatic function. Such medications may be used with caution as deemed essential for treatment, or if already in use prior to entry in the study without any effect on renal or hepatic function.
- Potent inhibitors or inducers of CYP1A2 or CYP2D6 (wash out period 7 days) – see [**Appendix C**](#).

5 BIOSPECIMEN COLLECTION

5.1 CORRELATIVE STUDIES FOR RESEARCH/PHARMACOKINETIC STUDIES

5.1.1 Peripheral blood and ascites

Blood will be acquired to study both the functionality of the patient's monocytes (*in vitro* killing assay), and to analyze the peripheral blood mononuclear cell (PBMC) compartment. 20 mL of whole blood will be collected into 10 mL EDTA lavender-top tubes. Blood will be diluted 1:1 in RPMI and placed on a Ficoll density gradient, and the PBMC buffy coat will be removed.

Further isolation of monocytes will be performed using negative magnetic bead based isolation, which will result in negatively isolated (untouched) monocytes. Based on our experiences isolating monocytes from the peripheral blood of patients with ovarian cancer (20 mL), we usually isolated between 2-4 million monocytes. 1.7 million monocytes are needed to assay them for cytotoxicity of target ovarian cancer cell lines (CaOV3 and OVCAR5) at four different concentrations of Sylatron® (Peginterferon alfa-2b) and Actimmune® (Interferon gamma-1b).

Another 20 mL of whole blood will be collected for the immune-phenotyping of the patients circulating immune system and PBMC will be isolated as stated above. Plasma will be stored for cytokine analysis and interferon antibodies. In our previous studies 20 mL of peripheral blood resulted in a range of 13 million to 27 million total PBMC. Using multi-parameter flow cytometry (FC) we will analyze T cell subsets, B cell subsets, myeloid compartment (macrophages, monocytes, dendritic cells), and NK cells (**Table 4**). We will use 5 separate panels with 10-12 antibodies per panel, with special emphasis on the detection of molecules associated with checkpoint blockade (PD1, PD2, PDL1, PDL2, CTLA4) to establish hypotheses for future clinical trials. In total, the panels will allow for the analysis of 137 distinct populations of immune cells. Blood from healthy donors acquired from the DTM will also be analyzed. The analysis of PBMC from healthy controls will allow comparisons between women affected with ovarian cancer and those without cancer. Using fluorescence minus one (FMO) gating strategy we will quantify the number of background events counted. These events will be subtracted from the total events counted to produce a quantification of true events. Measurement of 100,000 events per sample will enable us to perform statistical comparison of changes between healthy and affected, and changes within patients due to treatment. Counting a large number of events and using healthy age matched controls will allow us to statistically determine if there is a significant change between healthy donors, treatment groups, and between patients. When available, cells from ascites will be analyzed similarly.

Table 4. Cell Populations Analyzed by Flow Cytometry

Cell Type	Subsets
T cell	CD4, CD8, naïve, central memory, peripheral memory, effector, regulatory
B Cell	Naïve, memory, plasma
Monocyte	Classical, intermediate, non-classical
Dendritic Cell	cDC1, cDC2, pDC
Macrophages	M1, M2
NK Cell	Cytokine producers, cytotoxic

Excess apheresis fractions and ascites (if available) will be viably frozen for future functional studies.

Testing will be performed in the NIH laboratory, [name]. Specimen processing and storage will be performed by the Blood Processing Core (BPC). See Section **5.2**.

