10 STATISTICAL CONSIDERATIONS

Patients will be accrued in standard 3+3 dose escalation design, with expansion to 6 patients at the MTD and 10 additional patients at the MTD to allow for sufficient patients to perform correlative studies.

The 16 patients treated at the MTD (6 from dose escalation /MTD determination plus 10 additional patients) will be used to evaluate biologic correlates. With 16 patients, there would be 80% power to detect a change (either actual change or fold/relative change as appropriate) in the number of activated monocytes from baseline to after one cycle of treatment which would be equal to $\frac{3}{4}$ of a standard deviation of the difference measured (effect size 0.75) with a two-tailed 0.05 significance level paired t-test. If there are usable paired results from 10 patients instead of 16, this would result in the ability to detect a change with a 1.0 effect size based on the same parameters. In addition, a large number of other parameters will be obtained via flow cytometry and the changes from baseline to after one cycle of therapy will be determined. Given the large number of possible tests performed and the exploratory nature of the evaluation, there will not be any formal adjustment for multiple comparisons for these parameters. However, with 16 patients, there would be 80% power for any of the tests comparing baseline to post-treatment to detect a one SD difference between the two time points (effect size 1.0) with a two-tailed 0.01 significance level paired t-test; if there are 10 patients, there would be 80% power to detect a 1.0 effect size with a two-tailed 0.05 significance level paired t-test. The results of these exploratory tests will be reported in the context of the number of such tests performed.

The clinical response rate (in patients with measurable disease) and time to progression (in all patients) will also be estimated in a preliminary fashion. Appropriate confidence intervals will be provided along with fractions responding and a Kaplan-Meier curve of TTP.

It is estimated that up to 24 patients will be required to complete all 4 dose levels plus 10 additional patients will be needed at the MTD. Thus up to 34 evaluable patients may be required.

In order to allow for a small number of invaluable patients, the accrual ceiling will be set at 40 patients. Expected accrual rate is 1-2 patients per month. The DLT period is one cycle.

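### Section 5.1.1 offers the flow event count as the basis for significance between donors, treatment groups and patients, but events give no replication between people and section 10 supplies no person-level analysis for these comparisons

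*Combined protocol and SAP*

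**What the plan says.** Section 5.1.1 sets out flow cytometry in which "the panels will allow for the analysis of 137 distinct populations of immune cells". For comparison, "Blood from healthy donors acquired from the DTM will also be analyzed". Background events are estimated by fluorescence-minus-one gating and subtracted.

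Two sentences then tie inference to the event count. The first is "Measurement of 100,000 events per sample will enable us to perform statistical comparison of changes between healthy and affected"; it goes on to include treatment-related changes within patients. The second is "Counting a large number of events and using healthy age matched controls will allow us to statistically determine if there is a significant change", and the comparisons it covers are those "between healthy donors, treatment groups, and between patients". The section names no test, no unit of analysis and no number of healthy donors.

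Section 10 is explicit for one comparison only: "With 16 patients, there would be 80% power to detect a change" in activated monocytes from baseline to after one cycle, by paired t-test at effect size 0.75 and two-sided 0.05. The other flow parameters get the same paired treatment (effect size 1.0, two-sided 0.01 with 16 patients, or 0.05 with 10). They are labelled exploratory, are not adjusted for multiplicity, and are to be reported alongside the number of tests. Section 10 gives no analysis for patients versus healthy donors, for treatment groups, or for one patient against another.

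**The concern.** A measured cell frequency varies for two reasons: people differ, and a finite number of cells is counted. Raising the event count shrinks only the second source. Whether patients differ from donors, or one dose group from another, depends on how many people are measured and how much they vary. Section 5.1.1 credits the event count with something it cannot provide, and for these comparisons it is the only statistical basis in the plan.

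The clearest case is significance between individual patients. With one sample each at a time point, there is nothing except events from which to form a standard error.

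What is at stake is the exploratory immune work. The panels are meant to generate hypotheses for later trials, so differences called significant on event counts could shape follow-on work without any replication across people. Reporting results in the context of the number of tests addresses multiplicity, not a wrong unit.

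**Working it through.** **1. The plan's own figures (section 10).** Exact paired t-test power, noncentral t with n−1 degrees of freedom and noncentrality d√n:

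- n = 16, d = 0.75, two-sided 0.05: 80.1%
- n = 10, d = 1.0, two-sided 0.05: 80.3%
- n = 16, d = 1.0, two-sided 0.01: 83.5%; 16 is the smallest n that reaches 80%

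These reproduce, and n counts patients. The within-patient comparison therefore has the right unit.

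**2. What 100,000 events buys.** Input from section 5.1.1: n = 100,000 per sample. The 5% frequency is assumed, because no population frequencies are given for these blood panels.

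SE of one sample = √(0.05 × 0.95 / 100,000) = 0.00069, or 0.07 percentage points. If events were the replicates, two samples would differ at p<0.05 once they were 1.96 × √2 × 0.00069 = 0.0019 apart, or 0.19 points.

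Suppose the between-person CV is 30% (assumed), so SD = 0.015. The total SD of one person's value is √(0.015² + 0.00069²) = 0.01502. Counting infinitely many events would cut this by about 0.1%.

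**3. Two people from the same population, compared on events.** With SD = CV × p, the chance of p<0.05 is 2[1 − Φ(1.96 × SE / √(SD² + SE²))]. At p = 5%:

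- CV 10%: 1.96 × 0.00069 / 0.00505 = 0.268, giving 79%
- CV 30%: 0.090, giving 93%
- CV 50%: 0.054, giving 96%

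The CV is not in the documents, so the range is shown:

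| Frequency | CV 5% | CV 10% | CV 20% | CV 30% | CV 50% |
|---|---|---|---|---|---|
| 10% | 72% | 85% | 93% | 95% | 97% |
| 5% | 60% | 79% | 89% | 93% | 96% |
| 1% | 30% | 56% | 76% | 84% | 90% |
| 0.1% | 8% | 17% | 38% | 54% | 70% |

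**4. The protocol's own data (Appendix B, Table 8).** Final-product CD14/CD16 frequencies, fresh versus cryopreserved from the same donor, are 79.1 vs 87.6%, 79.1 vs 74.8% and 76.8 vs 80.6%. Event counts are not given; assume 100,000 each. With z = |p₁ − p₂| / √(2p̄(1 − p̄)/100,000), the results are 51.0, 22.8 and 20.8. Appendix B reads these data as showing no significant effect of cryopreservation. Taking the donor as the unit: differences +8.5, −4.3 and +3.8, mean 2.67, SD 6.47, t = 2.67 / (6.47/√3) = 0.71 on 2 df, p = 0.55. Three donors cannot establish equivalence. The example shows only how far the two units diverge, and that an event-level test would contradict the protocol's own reading.

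**5. What a person-level comparison could detect.** For 16 patients against an assumed 10 or 16 donors (normal approximation, 80% power, two-sided 0.05):

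- 10 donors: (1.96 + 0.842) × √(1/16 + 1/10) = 1.13 SD
- 16 donors: (1.96 + 0.842) × √(1/16 + 1/16) = 0.99 SD

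The number of donors drives this. The event count enters only through the small counting component of the SD.

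**The case against.** The strongest reply is that section 5.1.1 is laboratory prose, not an analysis plan. It pools no events and writes down no event-level test. Background subtraction to obtain a count of true events is compatible with one value per sample. The significance sentence also leans on healthy controls, who are other people. The only flow test specified anywhere, in section 10, uses the patient. All of this stands. A reader might infer that the plan treats cells as replicates; the documents do not say so, and the fault does not reach the paired analysis.

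Two further points stand in part. Patients are bled repeatedly (sections 3.4 and 5.1.4), so repeated samples could serve as weak replicates within a patient, and the wording about change between patients might mean comparing changes across patients. Events are the only possible replicates in the specific case of two patients with one sample each at a time point. The work is also exploratory, and per-sample values would allow a person-level analysis at any time, so it does not follow that the results would be beyond interpretation.

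What the reply does not remove is the stated claim. Section 5.1.1 twice presents the event count as what makes significance testing possible, and section 10 puts nothing in its place for donors, treatment groups or individual patients.

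**Conclusion.** The point holds as a mismatch between a stated inferential claim and what the design can support. Event count gives precision within a sample and no replication between people. Three of the comparisons named in section 5.1.1 have no person-level analysis in section 10, and significance between single patients at one time point has no valid basis.

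The size depends on inputs the documents do not give. At an assumed 5% frequency and CV of 10-50%, an event-level test would separate 79-96% of pairs. A reader might take this as a type I error rate. For a given pair it is not: when people vary, their true frequencies differ, and rejecting equality is correct but uninformative about groups or treatment. Nor does it follow that almost any two patients would differ on any given population, since at 0.1% frequency the range is 8-70% for CVs of 5-50%.

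This should be corrected, but it is confined to exploratory analyses. The paired tests in section 10 and the MTD, response and TTP objectives are unaffected.

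**What to change.** In sections 5.1.1 and 10:

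- State that the unit of analysis is the person, with one value per person per time point for each cell population.
- Keep the paired test for within-patient change. Name a two-sample t or rank test, with the person as the unit, for patients versus healthy donors and for dose groups. Give the number of donors.
- Drop claims of significance between individual patients and report those contrasts descriptively.
- Describe the 100,000 events as measurement precision only.

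This is a change of wording on data already to be collected, with no change to sampling, treatment or accrual. The downside is fewer nominally significant exploratory results.

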5.1.2 Plasma

5.1.2.1 Anti-interferon antibodies

At baseline and at the last cycle on study, patients will be monitored for the development of antibodies against interferons. Although IFN α and IFN γ are recombinant human proteins, repeated administration of these drugs can result in the development of antibodies against them [37, 38]. We will use two assays in our study to measure in participants the amount of: (a) binding antibodies to Sylatron® (Peginterferon alfa-2b) and Actimmune® (Interferon gamma-1b), and (b) neutralizing antibodies to both IFNs (antibodies that block the antiviral and antiproliferative function of the IFNs).

We will assay for IFN binding antibodies using a high-throughput multiplex assay [39]modified ELISA technique [38]. Briefly, plasma will be diluted 1:100 in PBS and incubated for 30 minutes with differentially fluorescing magnetic beads that have been covalently coupled to 2.5ug recombinant human IFN α (PBL Biomedical Laboratories; catalog 11101-2) or IFN γ (R&D Systems; catalog 285-IF-100/CF). Beads will be washed then incubated with 1ug/mL PE-labeled goat anti-human IgG (eBioscience; catalog 12-4998) for an additional 30 minutes before being washed again and run in a multiplex assay on the BioPlex X200 instrument (BioRad). Serum and ascitic fluid isolated from the patients and serum isolated from healthy age matched controls will be added and serially diluted as a negative control. For positive controls antibodies (WHO reference reagents) to IFN α -2b and IFN γ -1b will be used.

To detect IFN neutralizing antibody, plasma or ascites (when present) samples which are positive for IFN binding antibodies will be mixed with serial dilutions of Sylatron or Actimmune and then added to 96-well tissue culture plates seeded with 1×10^4 target cells (immortalized lung epithelial alveolar cells A549) [37]. WHO IFN international standards for IFNs α and γ and WHO neutralizing IFN antibody reference reagents will be used as controls. After 15-24 h incubation, encephalomyocarditis virus (EMCV) will be added to the cultures and incubated for an additional 24 h. If IFNs are present the virus will be unable to replicate allowing the cells to grow. If IFNs are not present (neutralized by antibody) the EMCV will kill the target cells. Percent cell viability of cell control can then be correlated to the WHO IFN international standards to calculate how much neutralizing antibody is present.

5.1.2.2 Multiplex Arrays

Plasma will be used for analysis of circulating cytokines. We will use multiplex cytokine arrays to analyze fluids compartment of blood and ascites. Multiplex allows for the analysis of up to 45 proteins including cytokines, chemokines, and growth factors with relatively small volumes of samples. We will use the Human ProcartaPlex Human Panel from eBioscience, or similar product.

Human Cytokine/ Chemokine/ Growth Factor Panel 1 (45 plex)	EPX450- 12171- 901	BDNF, EGF, Eotaxin (CCL11), FGF-2 (FGF basic), GM-CSF, GRO α (CXCL1), HGF, IFN γ , IFN α , IL-1RA, IL-1 β , IL-1a, IL-2, IL-4, IL-5, IL-6, IL-7, IL-8/CXCL8, IL-9, IL-10, IL-12 p70, IL-13, IL-15, IL-17A, IL-18, IL-21, IL-22, IL-23, IL-27, IL-31, IP-10 (CXCL10), LIF, MCP-1/CCL2, MIP-1 α /CCL3, MIP-1 β /CCL4, BNGF, PDGF-BB, PLGF, RANTES/CCL5, SCF, SDF1 α /CXCL12, TNF α , TNF β /LTA, VEGF-A, VEGF-D
---	-----------------------------------	---

5.1.3 Tissue biopsies (expansion phase)

Biopsies will be requested from all study participants in the expansion phase and will be obtained if clinically feasible. Tumor amenable to biopsy is not required for enrollment. If determined to be amenable to biopsy, however, tissue will be harvested by 18g core needle by an interventional radiologist. Up to 4 cores will be stored – 2 will be frozen immediately in OCT medium, and 2 will be formalin fixed and paraffin embedded. An amendment to this protocol (Amendment I, version date 02/11/2020) was submitted for Radiation Safety Committee and IRB approval prior to implementation of the expansion phase.

5.1.3.1 Multiparameter Microscopy

Correlative studies will include evaluation for in vivo evidence that interferons promote differentiation of monocytes to M1 macrophages resulting in tumor infiltration and death. Current advances in histology have enabled us to analyze up to 14 different proteins on a single histology slide. This technology can be used to study different cell populations and their interactions on the same section of tissue, instead of protein expression on serial sections. We will section biopsies and stain for: CD68, IL-12, CXCL10, NOS2, IL-10, and Arginase-1 (macrophage/monocyte); TRAIL, CD3, CD4, CD8 (T cell markers); FoxP3, PDL1, and PDL2 (Lymphocyte Inhibitory Markers). This analysis will allow us to quantify the presence and phenotype of immune cells in tissue before and after exposure to study agents.

5.1.4 Sampling Schedule

Test/assay	Volume blood (approx) or ascites	Type of tube	Collection point (+/- 48hrs)	Location of specimen analysis
Cellular component:	40 mL	EDTA * (10 mL tubes x 3)	D2 (cycles 1 and 2 only), Final visit	Women's Malignancies Branch (WMB; formerly [name] lab)
Plasma or ascites fluid: Anti-IFN antibodies	3 mL	EDTA ** (from above tubes)	C1D1, Final Visit	[name] lab, NIAID
Multiplex cytokine arrays	10 mL	(from above tubes)	D1 each cycle	FNLCR clinical services program
Biopsy (expansion cohort only)	NA	NA	D1 cycles 1 and 2, and at progression	WMB (formerly [name] lab)

* first 2 cycles, collect 30 mL (3 x 10-mL tubes)

** subsequent cycles, collect 1 x 10-mL tube only

5.2 SAMPLE STORAGE, TRACKING AND DISPOSITION

Research samples will be obtained from patients, as described in the protocol. Samples will be ordered in CRIS and tracked through a Clinical Trial Data Management system. Should a CRIS screen not be available, the CRIS downtime procedures will be followed. Samples will not be sent outside NIH without appropriate approvals and/or agreements, if required.

All specimens obtained in the protocol are used as defined in the protocol. Any specimens that are remaining at the completion of the protocol will be stored in the conditions described below. The study will remain open so long as sample or data analysis continues. Samples from consenting subjects will be stored until they are no longer of scientific value or if a subject withdraws consent for their continued use, at which time they will be destroyed.

If the patient withdraws consent the participant's data will be excluded from future distributions, but data that have already been distributed for approved research use will not be able to be retrieved.

The PI will record any loss or unanticipated destruction of samples as a deviation. Reporting will be per the requirements of section [7.2](#).

